however, are not universal and vary between patients and across surgical procedures. It is estimated that 20-30% of patients experience suboptimal weight loss or significant weight regain within the first few postoperative years. Reasons for this are not fully understood, but likely involve both physiological processes and behavioral factors (e.g., difficulty adhering to the dietary and physical activity recommendations made prior to surgery). Extreme Obesity More than one-third of American adults are obese, defined by a body mass index (BMI) of 30 kg/m2.1 Furthermore, 8.3% of women and 4.4% of men are extremely obese, defined by a BMI 40 kg/m2.1 Obesity, and extreme obesity in particular, is associated with major health complications including coronary heart disease, hypertension, type 2 diabetes mellitus, sleep apnea, and osteoarthritis.2-4 Surgical Treatment of Extreme Obesity Bariatric surgery is currently recommended for individuals 18 years and older with a BMI of 40 kg/m2 or those with a BMI of 35 kg/m2 in the presence of significant co-morbidities.5,6 Approximately 200,000 individuals are estimated to undergo bariatric surgery in the United States each year. The most common surgical procedures include the gastric bypass (GB), sleeve gastrectomy (SG), and adjustable gastric banding (AGB).7,8 As of 2013, the GB was the most common procedure in the United States, comprising 56% of all procedures; the SG comprised 36.3%.8 Anecdotal reports suggest that the SG is increasing in popularity while the AGB is now performed infrequently. With all three procedures, patients typically reach their maximum weight loss of 20-35% of body weight 12 months after surgery.3,4,9-16 These weight losses are associated with significant improvements in obesity-related co-morbidities and decreased risk of mortality.3,4,11,17-24 Despite these impressive results, studies have found that approximately 25% of patients who undergo bariatric surgery fail to reach or maintain the expected postoperative weight loss.25-27 Courcolous and colleagues, for example, observed that 23.6% of GB patients regained weight between postoperative year 1 and year 2. Less is known about the typical postoperative weight trajectory of patient who have undergone SG. Recent studies have suggested that weight regain is associated with deterioration of many of the health benefits seen with bariatric surgery.12,28-31 Psychosocial Status and Psychopathology in Candidates for Bariatric Surgery Extreme obesity is associated with a significant psychosocial burden, including impairments in quality of life, body image, sexual behavior and other areas of psychosocial functioning.32 While this distress is believed to contribute to the decision to have bariatric surgery, its impact on postoperative outcomes is less clear. At present, little is known about the physiological and behavioral contributions to success or failure of bariatric surgery.33 Regardless, weight regain after bariatric surgery is frequently attributed to preoperative psychosocial and behavioral factors.27,34-41 More specifically, there has been a great deal of interest in the presence of formal psychopathology in bariatric surgery patients and its potential contribution to postoperative outcomes.42-45 At least six studies have described rates of psychopathology in candidates for bariatric surgery using structured diagnostic instruments.46-51 Lifetime rates of any psychiatric diagnoses ranged from 36.8%-72.6%, higher than those reported in most studies of the general population. Mood disorders were the most frequent diagnoses, seen in 22.0%-54.8% of patients. Substance use disorders (SUDs) were found in up to 35.7% of patients and alcohol abuse or dependence in up to 33.2%. Binge eating disorder (BED), defined as eating an unusually large amount of food within a short period of time coupled with a loss of control over eating, has been diagnosed in 4.6% to 27.1% of patients. Current diagnoses (as compared with lifetime) were less common, reported in 20.9%-55.5% of candidates for surgery. Mood disorders were diagnosed in up to 31.5%. BED ranged from 3.4%-41.9%. Current substance use was seen in less than 2% of patients. (Note. The lower percentages of those with current psychopathology, as opposed to lifetime psychopathology, are expected.) While studies of the psychosocial characteristics of bariatric surgery candidates have been informative, they are not without limitations. Many studies have suffered from methodological concerns, including small sample sizes or lack of an appropriate comparison group. Further, establishing psychiatric diagnoses prior to bariatric surgery is challenging. Perioperative guidelines suggest that patients undergo an evaluation with a mental health professional prior to surgery3 and most third party payers require these evaluations. However, most programs do not use structured clinical interviews to establish diagnoses for clinical purposes.52,53 Several studies have suggested that candidates for bariatric surgery engage in impression management prior to surgery, in which they minimize reports of psychopathology to present themselves to the bariatric team in the most favorable light.54-56 To address this issue, assessment of psychiatric symptoms for research purposes is recommended to occur independently from the required clinical evaluation, as we will do in the proposed study. Nevertheless, studies focusing on the relationship between specific diagnoses and postoperative outcomes may fail to account for other psychological constructs that may be shared across diagnoses. Mood disorders, BED, and SUDs all share the common psychological construct of impulsivity, considered an important aspect of executive functioning. A lack of impulse control may contribute to the excessive weight gain seen in extreme obesity and may impact the results of bariatric surgery. Disinhibition and Impulsivity among Persons with Extreme Obesity Studies have suggested that individuals with obesity, and in particular those with extreme obesity presenting for bariatric surgery, show some deficits in executive functioning. For example, candidates for bariatric surgery have shown deficits in working memory, mental flexibility, motor speed and complex attention.57,58 These deficits could impact comprehension and retention of information presented to patients during the preoperative consultation process and, thus, negatively impact the ability to adhere to the dietary and behavioral changes required for an optimal postoperative outcome.45 At the same time, metabolic dysregulation, such as insulin resistance or hyperglycemeia seen in type 2 diabetes, also is associated with cognitive deficits, suggesting a potential physiological mechanism for the relationship.59-61 Dietary disinhibition, defined as a loss of control over eating, plays a central role in the overconsumption of food and, subsequently, the development of obesity.62.63 Disinhibition is similar to impulsivity, the term more commonly used in the substance use and smoking cessation literatures. Impulsivity is a multi-faceted construct and refers to the absence of the ability to inhibit an automatic behavior (otherwise known as response inhibition)64,65 and the tendency to discount future consequences in favor of more immediate outcomes (known as delay discounting).66,67 Similar to the role of disinhibition in obesity, impulsivity contributes to the development of and relapse with SUDs. Indeed, response inhibition and delay discounting are associated with both SUDs68-70 and obesity.71,72 Both also predict response to treatment for both SUDs73-75 and obesity.76 Chronic overeating and binge eating share several neurobiological and behavioral similarities with SUDs.77,78 In this regard, both may be viewed as behavioral disorders, in which intake (of food, alcohol, and/or drugs) escalates to a rate that is unhealthy and maladaptive. Nevertheless, the specific nature of the relationship between binge eating and substance use remains to be fully elucidated.79 There are similarities between binge eating and addictive disorders, including craving for the desired substance (drug or highly palatable food), a sense of loss of control when using, repeated attempts to control use despite clear adverse consequences, and the dedication of much time in obtaining and using the substance.80-82 Thus, the disinhibition observed with obesity and binge eating, the impulsivity seen with substance use disorders, and the emotional dysregulation associated with mood disorders all likely share commonalities (dashed lines in Figure 1) that may both contribute to the development of extreme obesity and also may be associated with weight loss (solid lines in Figure 1) and changes in psychosocial status after bariatric surgery. Psychosocial Status and Psychopathology after Bariatric Surgery In general, individuals who undergo bariatric surgery report dramatic improvements in psychosocial status and functioning postoperatively.83,84 The vast majority of patients report significant reductions in symptoms of depression and anxiety in the first postoperative year. They also report significant improvements in health and weight-related quality of life. Patients also report improvements in body image, sexual functioning, and relationship satisfaction.85-87 The relationship between preoperative psychopathology and postoperative outcomes is less robust.34,84 Livhits and colleagues reviewed this literature and concluded that the preoperative factors of BMI, BED, and the presence of personality disorders provided the strongest negative associations with postoperative weight loss.42 At least two studies have suggested that preoperative psychopathology, particularly mood and anxiety disorders, is associated with smaller weight postoperative weight losses.88,89 The relationship between BED and postoperative weight loss is unclear; some studies have found a relationship between preoperative BED and postoperative weight loss90.91 while others have not.92-94 Additionally, two studies have suggested that a history of substance abuse is associated with larger weight losses following bariatric surgery.95.96 The interpretation of this counterintuitive finding is that the selfregulation skills that help patients maintain their sobriety also help patients adhere to the demands of the recommended postoperative diet. Disinhibition and Impulsivity following Bariatric Surgery Encouragingly, studies have shown that there are improvements in executive functioning in persons with extreme obesity in the first two years after bariatric surgery.97,98 Postoperatively, patients typically report decreases in disinhibition and hunger, as well as increases in cognitive restraint.99,100 The physical aspects of bariatric surgery typically prevent individuals from eating the objectively large amount of food necessary to meet the diagnostic criteria of BED. However, many individuals continue to report the feeling of loss of control over their eating.44 The self-reported inability to control these impulses postoperatively is associated with smaller weight losses and greater emotional distress in the first few postoperative years.91,99,101,102 There is additional evidence that patients have difficulty with impulse control after surgery. A number of studies have suggested that there is an increased risk of substance abuse following bariatric surgery.101,103,104 King and colleagues,105 in their seminal investigation, found an increased rate of alcohol use disorder in the second postoperative year as compared to the year prior to surgery or in the first postoperative year. Other recent studies also have found increases in alcohol or composite substance abuse (drug, alcohol, or cigarettes) in the first two years after bariatric surgery.106-108 Postoperative substance use has been associated with smaller postoperative weight losses, postoperative nocturnal eating, and subjective hunger.109 Patients at

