
Characteristics of the Study Population

Target population

Adults aged 18-65 years old who plan to undergo one of two bariatric surgeries, either Rous-en-Y Gastric Bypass (RYGB) or Laparoscopic Sleeve Gastrectomy (LSG) at the University of Pennsylvania Health System. Based on our previous studies of bariatric surgery patients, we expect that approximately 80% of participants will be women and 20% of participants will be ethnic minorities.

Subjects enrolled by Penn Researchers 300

Subjects enrolled by Collaborating Researchers

0

Accrual

Participants will be recruited from the Bariatric Surgery Programs at the Hospital of the University of Pennsylvania and Presbyterian Medical Center, all part of Penn Medicine. We will enroll participants until a total of 300 adults have completed baseline visits. We anticipate that we will need to consent a larger number of participants in order to meet this enrollment goal. Based on our previous studies of bariatric surgery patients, we expect that approximately 80% of participants will be women and 20% of participants will be ethnic minorities. [name], Director of the Bariatric Surgery Program, conducts approximately 300 bariatric surgery operations per year. Additional surgeons in the Bariatric Surgery Program (at the Hospital of the University of Pennsylvania, Presbyterian Medical Center, and Pennsylvania Hospital) operate on approximately 200 patients per year. In order to increase the diversity and size of our sample, participants will also be recruited from the Temple Health Bariatric Surgery Program. The patient flow at Temple Health is similar to that of the Penn Health System (described below). Participants will be approached by the Research team during their pre-operative testing and education process.

Key inclusion criteria

We seek to enroll a sample of patients that is representative of those who present for bariatric surgery. We have based our exclusion criteria for the study largely on the clinical criteria used for bariatric surgery as well as our previous studies with bariatric patients. Inclusion Criteria: Adults aged 18-65 years old 18 years of age or above BMI of 35-60 kg/m2 (or 35 kg/m2 in the presence of significant weight-related comorbidities, including established coronary artery disease, established peripheral arterial disease, symptomatic carotid artery disease, sleep apnea, metabolic syndrome, cardiomyopathy, hypertension, and debilitating joint pain).

Key exclusion criteria

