
The following documents are currently attached to this item:

There are no documents attached for this item.

Deception

Does your project use deception? No

Analysis Plan

Analysis will be conducted using Stata 13.0 (Stata Corporation, College Station, TX). After the completion of quality assurance procedures, descriptive statistics will be summarized for all patients by predictor group (dichotomized). Data screening: Prior to performing analyses, standard data screening/ cleaning procedures will be applied. These procedures will: screen the data for data-entry errors; check for outliers; assess the extent and pattern of missing data; create all summary scores needed for analysis; and check that appropriate assumptions of normality are met. In all analyses, the assumptions underlying the application of all the statistical methods that are used will be examined, principally through the use of standardized residuals, influence diagnostics, and graphical displays. Image processing will include image quality assessment procedures that examine global and region of interest (ROI) based raw and processed temporal signal-to-noise ratio, absolute and relative motion, and signal spike count. Potential outliers will be identified in the cumulative sample by examining quality assessment measures and flagging for further investigation subjects greater than two standard deviations from the mean on any one measure (i.e., behavioral performance, image distortion and artifact, general linear model fit). The purpose of this evaluation is to determine whether the time series is likely valid, and, if so, it will remain. Otherwise it will be corrected, if feasible, or removed from the analysis. The final sample will be examined in a similar fashion to determine whether any subjects warrant data cleaning or require exclusion from the final statistical analysis. Analysis of repeated measures: Our four-session within-subject design will generate multiple outcome measures that belong to the Gaussian family, and we will therefore use standard repeated-measures analysis of variance (ANOVA). Imaging outcomes (perfusion and BOLD) will be modeled using standard voxel-based image analysis techniques (described below) that incorporate random effects. Other outcomes (weight loss, ratings) will be modeled using a linear mixed-effects models framework, using using Stata 13.0 (Stata Corporation, College Station, TX). We could use a population averaged approach such as generalized estimating equations. However, the mixed model approach will provide the flexibility to allow for different error variances for different sessions if necessary. Voxel-based image analysis has limited flexibility, particularly when adding multiple covariates and interaction. When needed, summary values (e.g., mean rCBF, mean BOLD% signal change) extracted from ROIs will be modeled in STATAs mixed-models framework. These models can be extended to include additional explanatory variables (e.g., weight change, heart rate, respirations, age). Primary Aim 1 We will take a mixed models approach. The main interest in this study is the Group x Time interaction, where Group will be a between-subjects factor and Time will be a categorical within-subjects factor. This can be interpreted as population averages (GEE fitting method). Hypothesis 1: We will fit a 2 (Group: Dichotomized Baseline Measures, Low, High) x 3 (Time: change from baseline to month 6, 12 and 24) mixed-effects model for change in weight. Hypothesis 2: We will fit a 2 (Group: Dichotomized difference scores, 6 Month minus Baseline, Low, High) x 2 (Time: change from baseline to months 12 and 24) mixedeffects model for change in weight. In addition, the mixed effects models will include adjustments for surgical procedure, gender, and time since surgery. We recognize that the change in weight could also be associated with effects of several pertinent patient characteristics. To this end, we will consider additional covariates (e.g. sociodemographic variables, comorbidities, medication use, tobacco use, and initial weight). For both hypotheses, we will explore the continuous version of our predictor variables, where in place of Group, we use the real values of the predictor. This yields a difference of slopes with respect to predictor value across time points. Secondary Aim 1 We will use confirmatory factor analysis to verify our expected natural groupings of individual measures into composite measures. We will specify 3 factors and use Varimax rotation. We will assemble composite scores for each of our constructs by summing the standardized score values. We will then standardize the composite score and outcome (change in weight at 24 months). We will estimate the partial correlations (direct and indirect) among individual measures, composites, and outcome in a path analysis as suggested by Figure 1 to estimate the fraction of variance in outcome accounted for by each of the constructs. Secondary Aim 2 The outcomes will consist of (continuous) changes in behavior from baseline. We will use correlation to examine the relationship of baseline impulsivity measures to changes at 6, 12 and 24 months. The exception is changes in diet composition. In this analysis, we will use multivariate regression methods,

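### Aim 1 tests Group x Time but specifies no Procedure x Time term, so a bypass-sleeve gap that changes over time would be credited to the predictor if procedure mix differs between Low and High groups

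*Combined protocol and SAP*

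**What the plan says.** Under Primary Aim 1, the Analysis Plan states: "The main interest in this study is the Group x Time interaction". Time is categorical. Hypothesis 1 is a "2 (Group: Dichotomized Baseline Measures, Low, High) x 3 (Time: change from baseline to month 6, 12 and 24" months) mixed model for change in weight. Hypothesis 2 splits patients on their change in the measure over the first 6 months and uses two visits, "x 2 (Time: change from baseline to months 12 and 24".

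Procedure appears in one sentence: "the mixed effects models will include adjustments for surgical procedure, gender, and time since surgery". The next step is optional: "we will consider additional covariates (e.g. sociodemographic variables, comorbidities, medication use, tobacco use, and initial weight" among the examples). No interaction of procedure, or of any other covariate, with Time is written, and no analysis stratified by procedure is planned.

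Two operations are eligible: "either Rous-en-Y Gastric Bypass (RYGB) or Laparoscopic Sleeve Gastrectomy (LSG"). The section on assigning subjects to groups says that there is no randomization. Procedure type is collected from the medical record (Subject recruitment).

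The Background says that surgical outcomes "are not universal and vary between patients and across surgical procedures", and of the sleeve: "Less is known about the typical postoperative weight trajectory of patient who have undergone SG". It also gives one range of maximum weight loss (20-35%) and one timing (12 months) for all procedures.

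**The concern.** The operation is the main driver of weight change here, and it is chosen rather than assigned. Low and High groups are formed from psychological and behavioral measures, so nothing in the design balances bypass and sleeve between them. In Hypothesis 2 the groups are defined by a change measured after the operation. Procedure could then influence group membership, although that is an inference that the documents do not state.

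The tested effect asks whether Low and High diverge over visits. A procedure term that is the same at every visit corrects the average level, not divergence. If the bypass-sleeve gap widens or narrows, and one group has more of one operation, Aim 1 could report divergence that belongs to the operation, or hide divergence that is real.

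**Working it through.** **Plan's own figure.** There is none for this adjustment. The sample size of 300 is said to be powered on Aim 1, but the text available gives no alpha, power, effect size, SD or dropout, so it cannot be reproduced.

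**Inputs.** From the documents: Group x Time as target; visits at 6, 12 and 24 months (12 and 24 in Hypothesis 2); two procedures; N = 300. Assumed, because the documents are silent: the procedure gap at each visit, g6, g12 and g24, in points of percent weight loss; the difference in procedure share between High and Low, D; and the residual SD. The true predictor effect is set to zero throughout.

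**Step 1: why a main effect does not help.** With complete data, Group x Time (24 vs 6) is the High-minus-Low difference in mean within-patient change from month 6 to month 24. Anything constant within a patient cancels from that change. Hence

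- bias in Group x Time (24 vs 6) = D x (g24 - g6);
- bias in the month-24 contrast, after a main effect has removed the average gap = D x (g24 - mean gap);
- bias in Hypothesis 2 Group x Time (24 vs 12) = D x (g24 - g12).

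Example with gaps of 3, 5 and 8 points and D = 0.20: 0.20 x (8 - 3) = 1.0 point; 0.20 x (8 - 5.33) = 0.53 point; and for Hypothesis 2, 0.20 x (8 - 5) = 0.6 point.

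**Step 2: check in a fitted mixed model.** One simulated data set of 300 used a random intercept, gaps of 2, 4 and 6 and procedure shares of 35% and 65%, so the expected bias is 0.30 x (6 - 2) = 1.2. A second data set had 20% missing at month 24. Estimates of Group x Time (24 vs 6), true value 0:

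| Model | Complete data | 20% missing at month 24 |
|---|---|---|
| No procedure term | 1.140 (SE 0.691) | 0.521 (SE 0.755) |
| Procedure main effect | 1.140 (SE 0.691) | 0.518 (SE 0.755) |
| Procedure x Time | -0.247 (SE 0.708) | -0.358 (SE 0.761) |

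The main effect changes nothing with complete data and almost nothing with dropout.

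**Step 3: range.** Bias in Group x Time (24 vs 6), with simulated type I error of the two-degree-of-freedom Group x Time test in brackets (nominal 5%, N = 300, residual SD 4, 1,500 replicates, main effect only):

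| Gap at 6/12/24 months | D = 0.10 | D = 0.20 | D = 0.30 |
|---|---|---|---|
| 3/3/3 (parallel) | 0 (4.2%) | 0 (6.5%) | 0 (4.9%) |
| 2/3/4 | 0.2 (5.9%) | 0.4 (7.2%) | 0.6 (12.5%) |
| 2/4/6 | 0.4 (8.5%) | 0.8 (17.9%) | 1.2 (32.3%) |
| 2/5/8 | 0.6 (10.0%) | 1.2 (33.1%) | 1.8 (59.7%) |

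For these evenly spaced gaps the month-24 contrast carries half the bias. Over the non-parallel rows, type I error runs from 4.8% to 35.0% with residual SD 6 and from 7.8% to 81.3% with SD 3. With equal mix (D = 0) it stays near 5% whatever the gaps.

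**Step 4: after the change.** With Procedure x Time the bias is 0.000 in every setting. Simulated type I error lies between 3.6% and 7.4%. The 7.4% cell, repeated with 6,000 replicates, gave 4.9%, so it was simulation noise.

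**Precision.** 0.708 / 0.691 = 1.025 with complete data; 0.761 / 0.755 = 1.008 with dropout.

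**The case against.** The plan never calls the procedure term additive, constant or a main effect, and it does not rule out interactions. A reader might infer that the plan commits to a constant offset. It does not: it leaves the form open. That stands, and the point is therefore put as an unspecified form with no interaction planned. The main-effect reading is still the natural one, because the plan writes interactions out where it wants them.

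A reader might also infer that the documents show diverging bypass and sleeve curves. They do not. Variation across procedures can be a difference in level only, which a main effect handles; limited knowledge of the sleeve is uncertainty, not divergence. The one statement about the shape of the curves gives the same range and the same time of maximum for all procedures. It does not establish parallel curves, but it gives no support to a gap that nearly triples. Nor do the documents link procedure choice to the predictors. All of this stands and limits the claim about size.

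The bias may also be modest. Against an assumed SD of 8, 0.53 point at month 24 is 0.53 / 8 = 0.07 SD, while 150 per group detects (1.960 + 0.842) x sqrt(2/150) = 0.32 SD (assumed two-sided 5%, 80% power). That is fair for the month-24 contrast. The interaction, however, is tested against within-patient variation, which may be smaller, and the false-positive rate rises as it falls.

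Finally, the plan includes descriptive summaries by predictor group and residual checks. These could reveal an unequal mix or a procedure-specific pattern, but they do not change the model. Adjustment for time since surgery does not close the gap either, because it is not specific to procedure.

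**Conclusion.** The point holds in a conditional form. The tested effect is Group x Time, no Procedure x Time term is specified, and a time-constant procedure term cannot protect that effect. A bias arises only if two conditions hold together: non-parallel procedure curves and unequal procedure mix. The documents quantify neither, so the size is unknown: 0 if either condition fails, and 0.2 to 1.8 points of percent weight loss for the interaction under the assumed inputs. It would be wrong to conclude that material bias is shown or likely. The case for acting is that the design does not exclude either condition and the remedy costs little. The open wording is also a weakness in itself: two analysts could follow the same sentence and report different Aim 1 results. Label: cheap improvement.

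**What to change.** In the Primary Aim 1 text, state that procedure performed (RYGB or LSG) enters both the Hypothesis 1 and Hypothesis 2 models with its interaction with categorical Time, and likewise in the continuous-predictor version. Read Group x Time and the month-24 group contrast from that model. Report procedure mix by Low and High group for each predictor. Gender, named in the same sentence, can be entered in the same form.

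For procedure the cost is one sentence, two extra parameters in Hypothesis 1 (three visits) and one in Hypothesis 2 (two visits). The loss of precision was 0.8% to 2.5% of the standard error in the two simulated data sets. No new data are needed, because procedure type is already collected.
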